¹ Cycle length = 21 days. For patients who do not achieve a CR or PR by the end of Cycle 6, the frequency of dosing may be increased and the cycle length will be 21-28 days. For patients whose response has plateaued for a minimum of 3 months, the dose frequency may be reduced, or treatment may be interrupted until relapse then restarted, and the cycle length will be the length of the dosing interval. See Section 7.1. For all patients who did not experience a treatment emergent abnormality in liver function tests (LFTs), defined as any grade abnormality in patients with normal value at baseline or any higher grade shift from baseline in patients with an abnormal baseline, or value more than 2x baseline if baseline was Grade ≥ 3 , or hepatic adverse events are present at imetelstat discontinuation, obtain LFT follow-up until 30 days from the last imetelstat dose. The length of the last cycle will be until 30 days after the last dose. For patients who experienced a treatment emergent abnormality in LFTs, as defined above, or hepatic adverse events are present at imetelstat discontinuation, obtain follow-up per test schedule (see Section 4 for details) until resolution to at least baseline grade or less than 2x baseline value if baseline was Grade ≥ 3 for at least 2 consecutive determinations. The length of the last cycle will be until the resolution is confirmed.

² Patients may continue to receive imetelstat study treatment for as long as they derive clinical benefit or until study end. The study will end when all subjects have discontinued study drug, the last patient enrolled has been treated for 5 years, or imetelstat is commercially available in the United States, whichever occurs first.

³ Except relapse that occurs during dose interruption. These patients may restart treatment at the physician's discretion per Section 7.1.

Figure 2: Schema – Arm B

(Note: Arm B permanently closed to accrual)

If a patient is deemed ineligible or a cancel, please refer to Section 13 for follow-up information.

[figure not shown]
¹ Cycle length = 21 days. For patients who do not achieve a CR or PR by the end of Cycle 6, the frequency of dosing may be increased and the cycle length will be 21-28 days. For patients whose response has plateaued for a minimum of 3 months, the dose frequency may be reduced, or treatment may be interrupted until relapse then restarted, and the cycle length will be the length of the dosing interval. See Section 7.1. For all patients who did not experience a treatment emergent abnormality in liver function tests (LFTs), defined as any grade abnormality in patients with normal value at baseline or any higher grade shift from baseline in patients with an abnormal baseline, or value more than 2x baseline if baseline was Grade ≥ 3 , or hepatic adverse events are present at imetelstat discontinuation, obtain LFT follow-up until 30 days from the last imetelstat dose. The length of the last cycle will be until 30 days after the last dose. For patients who experienced a treatment emergent abnormality in LFTs, as defined above, or hepatic adverse events are present at imetelstat discontinuation, obtain follow-up per test schedule (see Section 4 for details) until resolution to at least baseline grade or less than 2x baseline value if baseline was Grade ≥ 3 for at least 2 consecutive determinations. The length of the last cycle will be until the resolution is confirmed.

² Patients may continue to receive imetelstat study treatment for as long as they derive clinical benefit or until study end. The study will end when all subjects have discontinued study drug, the last patient enrolled has been treated for 5 years, or imetelstat is commercially available in the United States, whichever occurs first.

³ Except relapse that occurs during dose interruption. These patients may restart treatment at the physician's discretion per Section 7.1.

Figure 3: Schema – Arms C and D

(Note: Arms C and D permanently closed to accrual)

If a patient is deemed ineligible or a cancel, please refer to Section 13 for follow-up information.

¹ Cycle length = 28 days. For all patients who did not experience a treatment emergent abnormality in liver function tests (LFTs), defined as any grade abnormality in patients with normal value at baseline or any higher grade shift from baseline in patients with an abnormal baseline, or value more than 2x baseline if baseline was Grade ≥ 3 , or hepatic adverse events are present at imetelstat discontinuation, obtain LFT follow-up until 30 days from the last imetelstat dose. The length of the last cycle will be until 30 days after the last dose. For patients who experienced a treatment emergent abnormality in LFTs, as defined above, or hepatic adverse events are present at imetelstat discontinuation, obtain follow-up per test schedule (see Section 4 for details) until resolution to at least baseline grade or less than 2x baseline value if baseline was Grade ≥ 3 for at least 2 consecutive determinations. The length of the last cycle will be until the resolution is confirmed.

² For patients without response after the first two cycles, dosing might be increased to either Days 1, 3, 5 or Days 1, 3 every 2 to 4 weeks, per physician discretion. See Section 7.1.

[figure not shown]
³ For patients whose response has plateaued for a minimum of 3 months, the dose frequency may be reduced, or treatment may be interrupted until relapse then restarted, at the physician's discretion. See Section 7.1.

⁴ Patients may continue to receive imetelstat study treatment for as long as they derive clinical benefit or until study end. The study will end when all subjects have discontinued study drug, the last patient enrolled has been treated for 5 years, or imetelstat is commercially available in the United States, whichever occurs first.

⁵ Except relapse that occurs during dose interruption. These patients may restart treatment at the physician's discretion per Section 7.1.

Figure 4: Schema – Arm E

(Note: Arm E permanently closed to accrual) (myelofibrosis patients with spliceosome mutations or ring sideroblasts)

¹ Cycle length = 28 days. For all patients who did not experience a treatment emergent abnormality in liver function tests (LFTs), defined as any grade abnormality in patients with normal value at baseline or any higher grade shift from baseline in patients with an abnormal baseline, or value more than 2x baseline if baseline was Grade ≥ 3 , or hepatic adverse events are present at imetelstat discontinuation, obtain LFT follow-up until 30 days from the last imetelstat dose. The length of the last cycle will be until 30 days after the last dose. For patients who experienced a treatment emergent abnormality in LFTs, as defined above, or hepatic adverse events are present at imetelstat discontinuation, obtain follow-up per test schedule (see Section 4 for details) until resolution to at least baseline grade or less than 2x baseline value if baseline was Grade ≥ 3 for at least 2 consecutive determinations. The length of the last cycle will be until the resolution is confirmed.

² In patients who do not achieve CR or PR, by the end of Cycle 4, the frequency of dosing may be increased to every week or every 2 weeks, at the physician's discretion.

[figure not shown]
³ For patients whose response has plateaued, without signs of further improvement, for a minimum of 3 months, dosing frequency may be reduced to every 2 to 3 months, or treatment may be interrupted until relapse then restarted, at the physician's discretion.

⁴ Patients may continue to receive imetelstat study treatment for as long as they derive clinical benefit or until study end. The study will end when all subjects have discontinued study drug, the last patient enrolled has been treated for 5 years, or imetelstat is commercially available in the United States, whichever occurs first.

⁵ Except relapse that occurs during dose interruption. These patients may restart treatment at the physician's discretion per Section 7.1.

Figure 5: Schema – Arm F

(Note: Arm F permanently closed to accrual) (myelofibrosis patients without spliceosome mutations or ring sideroblasts)

[figure not shown]
¹ Cycle length = 28 days. For all patients who did not experience a treatment emergent abnormality in liver function tests (LFTs), defined as any grade abnormality in patients with normal value at baseline or any higher grade shift from baseline in patients with an abnormal baseline, or value more than 2x baseline if baseline was Grade ≥ 3 , or hepatic adverse events are present at imetelstat discontinuation, obtain LFT follow-up until 30 days from the last imetelstat dose. The length of the last cycle will be until 30 days after the last dose. For patients who experienced a treatment emergent abnormality in LFTs, as defined above, or hepatic adverse events are present at imetelstat discontinuation, obtain follow-up per test schedule (see Section 4 for details) until resolution to at least baseline grade or less than 2x baseline value if baseline was Grade ≥ 3 for at least 2 consecutive determinations. The length of the last cycle will be until the resolution is confirmed.

² In patients who do not achieve CR or PR, by the end of Cycle 4, the frequency of dosing may be increased to every two weeks, at the physician's discretion.

- ³ For patients whose response has plateaued, without signs of further improvement, for a minimum of 3 months, dosing may be reduced to Day 1 every 28 days or Days 1 and 3 every 2 to 3 months or treatment may be interrupted until relapse then restarted, all at the physician's discretion.
- ⁴ Patients may continue to receive imetelstat study treatment for as long as they derive clinical benefit or until study end. The study will end when all subjects have discontinued study drug, the last patient enrolled has been treated for 5 years, or imetelstat is commercially available in the United States, whichever occurs first.
- ⁵ Except relapse that occurs during dose interruption. These patients may restart treatment at the physician's discretion per Section 7.1.
- ⁶ If criteria still not met after Cycles 3 and 4, at the physician's discretion, dosing might be increased to Days 1, 3, and 5 every 28 days.

Figure 6: Schema – Arm G

(Note: Arm G permanently closed to accrual) (MDS/MPN or MDS patients with spliceosome mutations or ring sideroblasts)

¹ Cycle length = 28 days. For all patients who did not experience a treatment emergent abnormality in liver function tests (LFTs), defined as any grade abnormality in patients with normal value at baseline or any higher grade shift from baseline in patients with an abnormal baseline, or value more than 2x baseline if baseline was Grade ≥ 3 , or hepatic adverse events are present at imetelstat discontinuation, obtain LFT follow-up until 30 days from the last imetelstat dose. The length of the last cycle will be until 30 days after the last dose. For patients who experienced a treatment emergent abnormality in LFTs, as defined above, or hepatic adverse events are present at imetelstat discontinuation, obtain follow-up per test schedule (see Section 4 for details) until resolution to at least baseline grade or less than 2x baseline value if baseline was Grade ≥ 3 for at least 2 consecutive determinations. The length of the last cycle will be until the resolution is confirmed.

² In patients who do not achieve CR or PR, by the end of Cycle 4, the frequency of dosing may be increased to every week or every 2 weeks, at the physician's discretion.

³ For patients whose response has plateaued, without signs of further improvement, for a minimum of 3 months, dosing frequency may be reduced to every 2 to 3 months, or treatment may be interrupted until relapse, at the physician's discretion.

⁴ Patients may continue to receive imetelstat study treatment for as long as they derive clinical benefit or until study end. The study will end when all subjects have discontinued study drug, the last patient enrolled has been treated for 5 years, or imetelstat is commercially available in the United States, whichever occurs first.

⁵ Except relapse that occurs during dose interruption. These patients may restart treatment at the physician's discretion per Section 7.1.

PROTOCOL AMENDMENTS

Protocol Version	Issue Date
Geron Protocol Amendment 11 (prior to transfer to Janssen Research & Development)	31 Jul 2014
Amendment 12	21 Jan 2015
Amendment 13	5 Oct 2015

Amendments are listed beginning with the most recent amendment following transfer to Janssen Research & Development.

Amendment 13 (5 Oct 2015)

The overall reason for the amendment: To limit collection of follow-up study data to that critical for assessment of safety outcomes, and to allow subjects who are benefiting from imetelstat to continue to receive study treatment beyond 3 years.

Applicable Section(s)	Description of Change(s)
Rationale: To clarify and emphasize that additional hepatic laboratory surveillance is explicitly required for subjects in safety follow-up who had ongoing treatment-emergent abnormalities in LFTs or hepatic adverse events when imetelstat was discontinued,	
Figures 1-6	Revised “Event Monitoring” to “Event Monitoring/Hepatic Safety Monitoring” in the schematic diagrams for each treatment arm.
Rationale: To remove the limitation on duration of study treatment for patients who continue to derive clinical benefit beyond 3 years.	
Figures 1-6, footnotes 7.1.1.1 Arm A Treatment Schedule (footnote 1) 7.1.1.2 Arm B Treatment Schedule (footnote 1), 7.1.1.3 Arms C and D Treatment Schedule, (footnote 1) 7.1.1.4 Arms E and G Treatment Schedule, (footnote 1) 7.1.1.5 Arm F Treatment Schedule, (footnote 1) 8.1 Retreatment Criteria	Changed the possible duration of imetelstat study treatment beyond 3 years. Patients may continue to receive imetelstat study treatment for as long as they derive clinical benefit or until study end. The study will end when all subjects have discontinued study drug, the last patient enrolled has been treated for 5 years, or imetelstat is commercially available in the United States, whichever occurs first.
Rationale: The status of other imetelstat studies has changed.	
1.3.3 Clinical Experience with Imetelstat, Table 2	Database lock dates have been added for 4 Phase II imetelstat studies. The title of Study CP14B015 has been corrected to add “or Polycythemia Vera” and the study status has been changed from “Completed treatment (in safety follow up)” to “Completed”.

Rationale: To limit study procedures in the Extension Phase and at study completion to those needed for safety follow-up.

4 Test Schedule, Table 3	Physical examination for hepatomegaly and splenomegaly, and transfusion assessment removed as required assessments during the Extension Phase. Peripheral blood smear and IWG assessment of response removed as required assessments during the Extension Phase and at Study Completion/Early Termination. Urinalysis removed at Study Completion/Early termination.
4 Test Schedule, Table 3, footnote 9	Revised to delete chloride, bicarbonate, glucose, GGT, uric acid, amylase, and lipase from serum chemistry assessment.
4 Test Schedule, Table 3, footnote 10	Revised hematology assessment to replace differential count with absolute neutrophil count and to remove RBC count, MCV, MCH, MCHC, RDW, and MPV.
4 Test Schedule, Table 3, footnote 14	Clarified to allow a ± 7 -day window for hepatic event follow-up and redefined the end of the Event Monitoring Phase of the study from 5 years after registration for each subject to the time at which the last patient has completed study treatment. Follow-up during the Event Monitoring Phase can be completed via telephone call.

Rationale: To streamline and clarify hepatic monitoring.

4.1 Test Schedule for Hepatic Safety Monitoring, Table 4, footnote 3	CBC has been limited to WBC count, ANC, hemoglobin, and platelet count.
4.1 Test Schedule for Hepatic Safety Monitoring, Table 4	The footnote “Concomitant medications include alternate treatment for MPN/MDS” has been deleted; remaining footnotes have been renumbered accordingly.

Rationale: To clarify requirements for study drug dose modification.

8.2 Dose Reduction	Sentence added to the end of the first paragraph clarifying that once an imetelstat dose reduction has occurred, the dose should not be subsequently re-escalated.
--------------------	--

Rationale: Update description of drug preparation procedures. Reconstitution time is estimated at 15 minutes based on an updated product description.

15.1.3 Preparation and Storage	Text describing lyophilized imetelstat as reconstituting easily has been deleted.
--------------------------------	---

Rationale: Minor errors were noted.

Throughout the protocol	Minor grammatical, formatting, or typographical changes were made.
-------------------------	--

Amendment 12 (21Jan 2015)

The overall reason for the amendment: The overall reason for the amendment is to transfer sponsorship of this study from Geron to Janssen Research & Development and to update safety reporting accordingly.

Applicable Section(s)	Description of Change(s)
Rationale: To update the language in the protocol to indicate the transfer of sponsorship from Geron to Janssen Research & Development and to establish the safety reporting procedures under the new sponsorship.	
10.1. Safety Parameters and Definitions; 10.3.1.9. Pregnancy; 10.6. Post-Study Adverse Events	Language changed to indicate transfer of sponsorship.
10.4.1. Reporting Requirements for Fatal/Life Threatening SAEs Related to Investigational Product	Deleted the former medical monitor contact information and replaced with the following: The names (and corresponding telephone numbers) of the individuals who should be contacted regarding safety issues or questions regarding the study are listed on the Contact Information page(s), which will be provided as a separate document.
10.4.2. Reporting Requirements for All SAEs	Deleted the former procedures for reporting SAEs and replaced with the new procedures.
16.7. Data and Safety Monitoring	Updated the membership of the safety review committee and updated the following text (bold text indicates additions; strikeout indicates deletions): The Medical Monitor study responsible physician or Drug Safety Scientist safety physician may convene a meeting sooner should any concerns arise from review of data or from the Investigator safety physician. Added text to indicate that an independent hepatic safety panel will review emergent relevant safety data if needed.

Rationale: To align the current protocol with the administrative amendment memorandum that was issued by Geron on 12 Sep 2014.

4. Test Schedule, Table 3, footnote 6	Removed the check mark in the table for an abdominal ultrasound at study completion or early termination (\pm 1 week); Revised the footnote to indicate that a Doppler ultrasound of abdomen will be performed post baseline only as clinically indicated at the discretion of the investigator.
4. Test Schedule, Table 3, footnote 9; 4.1. Test Schedule for hepatic safety monitoring and follow up after discontinuing imetelstat, Table 4, footnote 3	Revised the text to state that serum haptoglobin and reticulocyte count should be performed only if clinically indicated.

Rationale: Included information regarding the lift of the clinical hold by the U.S. FDA.

1.3.4.4. Hepatobiliary Events	Added: Following a complete response submitted by Geron, the clinical hold was lifted by the U.S. FDA on 31 October 2014.
-------------------------------	---

Rationale: To update information regarding Phase II trials with imetelstat.

1.3.3. Clinical Experience with Imetelstat, Table 2 The study status of protocol number CP14B013 was marked as completed.

Rationale: Minor errors were noted.

Throughout the protocol Minor grammatical, formatting, or spelling changes were made.

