4. TEST SCHEDULE

All routine assessments must be performed within \pm 3 days of the day indicated on the Visit Schedule (except for screening).

Table 3: Test Schedule: Core Phase = Cycle 1 – Cycle 9; Extension Phase = Cycle 10 and Beyond

Assessment	Screening (\leq 14 days Prior to registration)	\leq 24 hours before each imetelstat infusion Cycles 1-9 or end of cycle during interruption ¹	Weekly in first 2 cycles	End of Cycle 3	End of Cycle 9	Every Cycle in extension phase prior to infusion (Cycles 10 and beyond) ¹	At study completion or early termination (\pm 1 week) ²	Event Monitoring Every 3 mo until PD or subsequent treatment for MF Every 6mo after PD or subsequent treatment for MF ¹⁴
Physical examination including weight (height at screening) ^{3,4}	X			X	X		X	
Physical examination for hepatomegaly and splenomegaly ^{3,4}	X	X			X		X	
Transfusion Assessment	X	X						
Record adverse events ⁴	X	X			X	X	X	
Record concomitant medication		X				X	X	
ECOG performance status (Appendix D) ⁴	X	X			X		X	
12-lead ECG	X							
Chest x-ray	X							
Serum pregnancy test ^{4,5}	X	X				X		
Abdominal Ultrasound ⁶	X							
Urinalysis ⁷	X			X	X			

Assessment	Screening (≤14 days Prior to registration)	≤24 hours before each imtelstat infusion Cycles 1-9 or end of cycle during interruption ¹	Weekly in first 2 cycles	End of Cycle 3	End of Cycle 9	Every Cycle in extension phase prior to infusion (Cycles 10 and beyond) ¹	At study completion or early termination (± 1 week) ²	Event Monitoring Every 3 mo until PD or subsequent treatment for MF Every 6mo after PD or subsequent treatment for MF ¹⁴
Temperature and vital signs ⁸	X	X			X	X	X	
Serum chemistry ^{4,9}	X	X	X		X	X	X	
Serum calcium, phosphorus, magnesium, total protein	X			X	X		X	
CBC ^{4,10}	X	X	X		X	X	X	
Peripheral blood smear ⁴	X	X	X		X			
Serum Epo level	X			X	X			
International Working Group (IWG) Assessment of response ⁴		X			X			
INR (or PT) and aPTT ^{7,4}	X	X						
Bone marrow biopsy and aspirate with cytogenetic and JAK2 V617F studies ¹¹	X ¹²				X ^{12,13}			
Follow-up for survival and disease status and information of subsequent treatment for MF ¹⁴								X

R Samples may be used by Mayo Clinic or sponsor for research tests that include granulocyte JAK2V617F allele burden measurement, plasma cytokine analysis and other tests that are deemed insightful.

CBC = complete blood count

¹ In case of interruption, a cycle will be 3 months while treatment is held.

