13. TREATMENT/FOLLOW-UP DECISION AT EVALUATION OF PATIENT

Patients who are CR, PR, CI, or SD will continue treatment per protocol.

Patients will be discontinued from treatment and go to event-monitoring phase per Section 4 for any of the following reasons:

- Disease progression (Except relapse that occurs during dose interruption).
- Leukemic transformation (as per WHO criteria)
- Any clinical adverse event, laboratory abnormality, intercurrent illness or other medical condition or situation which occurs such that continued participation in the study would not be in the best interest of the participant
- Hepatotoxicity criteria for treatment discontinuation (see Section [8.2.1](#))
- Pregnancy
- Diagnosis of positive status for HIV or hepatitis B or C
- Continued failure to comply with study procedures or use of the drug as specified in the study protocol such that continued participation in the study would not be in the best interest of the participant
- Withdrawal of consent
- Initiation of non-protocol therapies
- Administrative decision by investigator or sponsor

A patient is deemed *ineligible* if after registration, it is determined that at the time of registration, the patient did not satisfy each and every eligibility criteria for study entry. The patient may continue treatment off-protocol at the discretion of the physician as long as there are no safety concerns, and the patient was properly registered. The patient will go directly to the event-monitoring phase of the study.

- If the patient received treatment, all data up until the point of confirmation of ineligibility must be submitted. Event monitoring will be required per Section 4 of the protocol.
- If the patient never received treatment, on-study material and the End of Active Treatment/Cancel Notification Form must be submitted. No further data submission is necessary.

A patient is deemed a *major violation*, if protocol requirements regarding treatment in Cycle 1 of the initial therapy are severely violated that evaluability for primary end point is questionable. All data up until the point of confirmation of a major violation must be submitted. The patient will go directly to the event-monitoring phase of the study. The patient may continue treatment off-protocol at the discretion of the physician as long as there are no safety concerns, and the patient was properly registered. Event monitoring will be required per Section 4 of the protocol.

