4.3. Major Secondary Endpoints

4.3.1. Definition

Spleen Response

Spleen response is defined as either a minimum 50% reduction in palpable splenomegaly of a spleen that is at least 10 cm at baseline or a spleen that is palpable at less than 10 cm but more than 5 cm at baseline becomes not palpable.

Transfusion Independence

Transfusion dependency is defined by a history of at least 2 units of red blood cell transfusions in the last month or a baseline hemoglobin level of less than 85 g/L that was not associated with clinically overt bleeding. For a transfusion dependent subject, transfusion independence is defined as he/she met either of the following conditions:

- Received no more than 1 unit of red blood cell transfusions in a rolling time interval of 30 days or more.
- Had a hemoglobin level increase over baseline more than 2g/dl if his/her baseline hemoglobin level was less than 85 g/L and received no transfusion.

Time to Response (TTR)

Time to response is defined as the duration from Study Day 1 to the earliest date that a response is first documented. For non-responders, it will be censored at the date of progressive disease/relapse or the date of the last adequate assessment, whichever comes first.

Duration of Response (DoR)

Duration of response is defined for responders as the interval from date of the initial documentation of a response to the date of first documented evidence of disease progression (or relapse for subjects who experience CR). For those subjects who are still without progression/relapse, DoR will be censored at the last adequate assessment.

Overall Survival (OS)

OS is defined as the interval from Study Day 1 to the date of death from any cause. Survival time of living subjects will be censored on the last date a subject is known to be alive or lost to follow-up.

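### The SAP has no duration-of-response rule for relapse during a planned drug stop: read literally, that relapse ends DoR for CR subjects but not for myelofibrosis subjects with CI or PR

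*Protocol*

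**What the plan says.** **Protocol.** Figures 1 to 6 and the schedules in Section 7.1.1 offer a planned stop in every arm. In Arms E to G the condition reads "For patients whose response has plateaued, without signs of further improvement, for a minimum of 3 months"; Arms A to D use the same 3-month minimum. Figure 4, footnote 3 (Arm E) then says "treatment may be interrupted until relapse then restarted, at the physician's discretion". The Arm G schema says only "treatment may be interrupted until relapse, at the physician's discretion", but its footnote 5 and the second footnote to Table 5 allow restart. The schema footnotes add "Except relapse that occurs during dose interruption. These patients may restart treatment at the physician's discretion per Section 7.1". Section 13 lists as a reason to stop treatment "Disease progression (Except relapse that occurs during dose interruption".

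**SAP.** In 4.3.1, DoR runs from first documented response to "the date of first documented evidence of disease progression (or relapse for subjects who experience CR". The next sentence censors, at the last adequate assessment, subjects with neither progression nor relapse, and there relapse is not limited to CR. SAP 4.3.2 gives a Kaplan-Meier median with a Brookmeyer-Crowley interval. Neither section mentions planned interruption, restart or a regained response. Protocol 16.4.4 names the same method without defining the event, and the overview of Protocol Section 16 says the SAP supersedes the protocol's analyses.

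**The concern.** Onset and durability of response are a stated secondary objective in both documents. A reader will take a median DoR as how long response lasts on imetelstat. Here some responders will have been taken off drug on purpose, with relapse as the trigger for restarting. The SAP does not say whether that relapse is a loss of response, and its definition gives different answers for different responders. The reported median would then depend on how often physicians chose to interrupt and on the mix of CR, PR and CI, as well as on the drug.

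**Working it through.** The plan states no DoR figure (no assumed median, number of responders or interruption rate), so there is nothing to reproduce. The check is textual, followed by an illustration.

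**1. What an off-drug loss of response does to DoR.** SAP 4.2.1 counts CI, PR and CR as response in Arms A, B, E and F; HI, PR and CR in Arm G; and a durable fall in blasts in Arm D. Protocol Table 15 defines relapse after CR, PR or CI and lists it separately from progressive disease.

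| Responder | Protocol criterion for loss | Event under the SAP definition? |
|---|---|---|
| CR, MF arms | Table 15 relapse | Yes, same as on drug |
| PR or CI, MF arms | Table 15 relapse | No, unless progressive disease is also met |
| CR, Arm G | Table 16 relapse | Yes |
| PR, Arm G | Table 16 relapse | Only if progression is met; the count, hemoglobin and transfusion criteria overlap, so some losses qualify |
| HI, Arm G | Table 17, progression and relapse in one category | Unclear |
| Arm D | No relapse criterion tied to the Arm D response | No CR category in the response definition; progression only |

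The gap for CI can be wide. Take a spleen palpable at 12 cm at baseline (my example) that shrinks to 6 cm. That is a 50% decrease and a spleen response. If it regrows to 12 cm off drug and stays there for a month, Table 15 calls it relapse. Progressive disease for a baseline above 10 cm needs a 50% increase over the pre-treatment value: 12 × 1.5 = 18 cm. Until then the literal SAP rule records no spleen-based event.

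**2. Size if relapse ended DoR for every responder.** All inputs are assumed: on-drug median *m*, off-drug median *h*, interruption at month 6, share interrupted *q*.

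- Not interrupted: S₁(t) = 2^(−t/m).
- Interrupted: S₂(t) = S₁(t) up to month 6, then 2^(−6/m) × 2^(−(t−6)/h).
- Pooled: S(t) = (1−q)S₁(t) + qS₂(t), solved for S = 0.5.

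Check for m = 18, h = 6, q = 50%, t = 12.4: S₁ = 0.620; S₂ = 0.794 × 0.477 = 0.379; their average is 0.500.

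| m / h (months) | q = 0 | q = 25% | q = 50% |
|---|---|---|---|
| 12 / 6 | 12.0 | 10.9 | 10.1 |
| 12 / 9 | 12.0 | 11.6 | 11.2 |
| 12 / 12 | 12.0 | 12.0 | 12.0 |
| 18 / 6 | 18.0 | 14.6 | 12.4 |
| 18 / 12 | 18.0 | 16.8 | 15.7 |
| 24 / 6 | 24.0 | 17.9 | 14.0 |

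This table does not describe the SAP as written.

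**3. Size under the literal rule.** Let *c* be the share of responders with CR. Non-CR responders have an event only at progression, with an assumed median of 36 months: S(t) = c × S_pooled(t) + (1−c) × 2^(−t/36), with m = 18 and h = 6.

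| c | q = 0 | q = 25% | q = 50% |
|---|---|---|---|
| 0 | 36.0 | 36.0 | 36.0 |
| 25% | 30.0 | 28.5 | 26.9 |
| 50% | 25.0 | 22.3 | 19.7 |
| 100% | 18.0 | 14.6 | 12.4 |

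With no CRs, the median does not move with the share interrupted. At q = 50% the same pattern of relapse gives 12.4 months if relapse counts for everyone, 19.7 if half the responders are CR, and 36.0 if none are. Those differences come from the event rule and the assumed 36 months, not from how long response lasts.

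**The case against.** **No contradiction between the documents.** Section 13 and the schema footnotes decide who stays on treatment; they are not efficacy rules. Counting relapse whatever the dosing status is an ordinary treatment-strategy definition. This stands. The fault is that the SAP neither says it is doing this nor does it for CI and PR.

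**A stronger reading.** A reader might infer that every drug-free period ends in a DoR event, so that planned stops always shorten the median. The documents do not support that. Relapse is an event only for CR subjects, follow-up can end before relapse, and for CI and PR in the MF arms the literal rule lengthens DoR relative to the protocol's own relapse criterion.

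**Visit spacing.** "In case of interruption, a cycle will be 3 months while treatment is held", so off-drug relapse is dated coarsely. But patients on reduced dosing can also have cycles of 84 days, and Table 3 marks no IWG response assessment in the extension phase, although Section 8.1 still speaks of efficacy evaluation each cycle. Coarse dating is therefore not specific to interruption, and an interval-censored analysis would add little.

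**Limited consequence.** DoR is secondary and descriptive, arms are evaluated independently, no between-arm comparison of DoR is planned, and 80 subjects were enrolled. Dose adjustments with reasons (SAP 3.3) and response by cycle (SAP 4.2.2) are already listed. All of this stands and limits the weight of the point. Listings do not, however, tell a reader what the reported median means.

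**Conclusion.** The concern holds in this form. SAP 4.3.1 leaves planned interruption unaddressed. Its definition treats the same off-drug relapse as an event for CR subjects and, in the MF arms, as no event for CI or PR subjects without progressive disease. Its censoring sentence does not agree with that limit. Median DoR therefore mixes on-drug durability with time to relapse after a planned stop, and misses some losses of response altogether. The distortion can go either way depending on response category.

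Its size cannot be stated. The documents give no interruption rate, CR share or relapse rates, and the effect is nil if nobody was interrupted. The illustrated medians rest wholly on assumed inputs; the 18.0, 14.6 and 12.4 month series applies only if relapse ends DoR for every responder. The primary response rate is not affected.

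**What to change.** In SAP 4.3.1 and 4.3.2:

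1. Define the DoR event for each response category (CR, PR, CI, HI and the Arm D response). Count loss of response or relapse by the protocol's criteria for all responders, and state that relapse during a planned interruption counts (a treatment-strategy DoR). Arm D needs an explicit criterion for loss of its blast response. Make the censoring sentence agree.
2. Beside that DoR, not in its place, add a supportive Kaplan-Meier DoR censored at the last assessment before a planned interruption.
3. Report by arm the number of responders interrupted, time off drug to relapse, number restarted and number who responded again.

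An interval-censored sensitivity analysis is optional.

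**Cost.** SAP wording and a few outputs from dosing and per-cycle response data already planned for listing. Item 1 changes the planned event for CI and PR and should be recorded as a change. Item 2 is informatively censored, because only stable responders are interrupted, and should be labelled so. Item 3 may be incomplete for interruptions in the extension phase, where Table 3 schedules no IWG assessment. No change to the clinical interruption rule is proposed.
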